## 10. STATISTICAL METHODS

### 10.1. Primary endpoint

- Immune responses against *N. meningitidis* serogroup B\* test strains and *N. meningitidis* serogroups A, C, W-135, and Y, as measured by hSBA, 1 month after the last vaccination in all study groups
  - hSBA GMTs against each of the *N. meningitidis* serogroup B test strains and against *N. meningitidis* serogroups A, C, W-135, and Y
  - hSBA GMTs against all of *N. meningitidis* serogroup B test strains (pooled)
  - Percentage of subjects with hSBA titers  $\geq$  the lower limit of quantitation (LLOQ) against each of the *N. meningitidis* serogroup B test strains and against *N. meningitidis* serogroups A, C, W-135, and Y
  - Percentage of subjects with a 4-fold increase in hSBA titers against *N. meningitidis* serogroups B test strains and against *N. meningitidis* serogroups A, C, W-135, and Y
  - hSBA geometric mean ratios (GMRs) against each of the *N. meningitidis* serogroup B test strains and against *N. meningitidis* serogroups A, C, W-135, and Y at 1 month after the last vaccination against baseline (Day 1)

\*Serogroup B strains that will be tested are M14459 (factor H binding protein; fHbp), 96217 (Neisserial adhesin A; NadA), NZ98/254 (PorA), and M07-0241084 (Neisseria heparin binding antigen; NHBA) and will be pooled to estimate the effect of immune interference due to stress to lymph nodes.

Note: A 4-fold rise is defined as: a) for individuals whose pre-vaccination titers are  $<$  the limit of detection (LOD), the post-vaccination titers must be  $\geq$ 4-fold the LOD or  $\geq$  the LLOQ, whichever is greater; b) for individuals whose pre-vaccination titers are  $\geq$  the LOD and  $<$  the LLOQ, the post-vaccination titers must be at least 4 times the LLOQ; and c) for individuals whose pre-vaccination titers are  $\geq$  the LLOQ, the post-vaccination titers must be at least 4 times the pre-vaccination titer.

The ratios of GMTs between study groups will be analyzed to evaluate effect of treatment as described below:

- a. Immune interference due to stress to lymph nodes (lymph-node effect) in rMenBOMV+ACWY\_S versus rMenBOMV+ACWY\_D study groups, on the pooled B strains, and individually by serogroup A, C, W-135, Y, and B test strains.
- b. Other unknown interference in the MenABCWY versus rMenBOMV+ACWY\_S study groups, by serogroup A, C, W-135, Y, and B test strains.

- c. The difference in immune response compared to control groups in rMenBOMV+ACWY\_S versus rMenBOMV and MenACWY, rMenBOMV+ACWY\_D versus rMenBOMV and MenACWY, and MenABCWY versus rMenBOMV and MenACWY study groups, by serogroup A, C, W-135, Y, and B test strains.

## 10.2. Secondary endpoints

### Immunogenicity Endpoints

- Immune responses against *N. meningitidis* serogroup B\* test strains and *N. meningitidis* serogroups A, C, W-135, and Y, as measured by hSBA, 1 month after the first vaccination in all groups (except for subjects in the MenACWY group)
  - hSBA GMTs against each of the *N. meningitidis* serogroup B test strains and against *N. meningitidis* serogroups A, C, W-135, and Y
  - hSBA GMTs against all of *N. meningitidis* serogroup B test strains (pooled)
  - Percentage of subjects with hSBA titers  $\geq$  the LLOQ against each of the *N. meningitidis* serogroup B test strains and against *N. meningitidis* serogroups A, C, W-135, and Y
  - Percentage of subjects with a 4-fold increase in hSBA titers against *N. meningitidis* serogroups B test strains and against *N. meningitidis* serogroups A, C, W-135, and Y
  - hSBA GMRs against each of the *N. meningitidis* serogroup B test strains and against *N. meningitidis* serogroups A, C, W-135, and Y at 1 month after the first vaccination against baseline (Day 1)

\*Serogroup B tests strains that will be tested are M14459 (fHbp), 96217 (NadA), NZ98/254 (PorA), and M07-0241084 (NHBA).

Notes, as described in Section 10.1, also apply to the secondary endpoints.

The ratios of GMTs between study groups will be analyzed to evaluate effect of treatment as described below:

- a. Immune interference due to stress to lymph nodes (lymph-node effect) in rMenBOMV+ACWY\_S versus rMenBOMV+ACWY\_D study groups, on the pooled B strains, and individually by serogroup A, C, W-135, Y, and B test strains.
- b. Other unknown interference in MenABCWY versus rMenBOMV+ACWY\_S study groups, by serogroup A, C, W-135, Y, and B test strains.
- c. The difference in immune response compared to control groups in rMenBOMV+ACWY\_S versus rMenBOMV, rMenBOMV+ACWY\_D versus rMenBOMV, and MenABCWY versus rMenBOMV study groups, by serogroup B test strains.

## Safety Endpoints

- Solicited local and systemic AEs in all study groups
  - Occurrence of solicited local and systemic AEs during the 7 days (including the day of vaccination) after each vaccination (Day 1 to Day 7 and Day 61 to Day 67 [Day 1 to Day 7 only for subjects in the MenACWY group])
- Unsolicited AEs in all study groups
  - Occurrence of unsolicited AEs during the 30 days (including the day of vaccination) after each vaccination (Day 1 to Day 31 and Day 61 to Day 91 [Day 1 to Day 31 only for subjects in the MenACWY group])
- SAEs, medically attended AEs, AEs leading to withdrawal, and AESIs, in all study groups from informed consent signature to Visit 4 (Day 91)

### **10.3. *Tertiary endpoint***

*Endpoints related to the tertiary objective will be described in a separate statistical analysis plan. (Amended 29 Aug 2018)*

### **10.4. *Determination of sample size***

The sample size is for exploratory statistical analysis purposes only. There are no formal confirmatory hypotheses to be tested. The text in this section describes what can be observed with the current sample size.

Sample size calculation was performed using PASS 12 and SAS 9.2 (SAS Institute Inc., Cary, NC, USA).

The potential immune interference due to immunological stress to lymph nodes is assumed to result in decreases to all of the 4 B test strains but to various extents. In a previous study (MenABCWY-011 [V102\_15]), the GMT ratios ranged from 74% (-0.13 on log10 scale) to 50% (-0.3 log10 scale) with a mean of 64% (-0.19 on log10 scale). Because of this consistent decrease in GMT ratios in the MenABCWY group in comparison to the MenB group across the 4 serogroups, the presence of the lymph-node effect will be tested globally on all the serogroups together. A multivariate analysis of V102\_15 data provided an estimate of  $\sigma = 0.435$  (on log10 scale) for the standard deviation (SD) of the averaged GMTs across the 4 serogroups of the MenABCWY arm. That variability is higher than what would be expected by dividing the variance of a single serogroup by 4 due to the correlations existing between serogroups.

Therefore, assuming a SD of  $\sigma = 0.435$  (in log form), group sample sizes of 100 in each study group will achieve a power of approximately 80% to reject the null hypothesis of equal means when the population mean difference is -0.130 (log GMT ratio 74%) with a SD of 0.435 for both groups and a significance level (alpha) of 10% using a 1-sided 2-sample equal-variance t-test. This calculation ignores the potential correlation that might exist between serogroups of the MenABCWY when pooled together.

The numerical results for the 2-sample t-test assuming equal variance (alternative hypothesis:  $\delta < 0$ ) is shown in [Table 14](#).

**Table 14      Sample size calculation results**

Power	N1	N2	$\delta$	$\sigma$	Alpha	Beta
0.650	100	100	-0.145	0.435	0.025	0.350
0.759	100	100	-0.145	0.435	0.050	0.241
0.819	100	100	-0.145	0.435	0.075	0.181
0.858	100	100	-0.145	0.435	0.100	0.142
0.620	100	100	-0.140	0.435	0.025	0.380
0.733	100	100	-0.140	0.435	0.050	0.267
0.797	100	100	-0.140	0.435	0.075	0.203
0.839	100	100	-0.140	0.435	0.100	0.161
0.589	100	100	-0.135	0.435	0.025	0.411
0.706	100	100	-0.135	0.435	0.050	0.294
0.773	100	100	-0.135	0.435	0.075	0.227
0.818	100	100	-0.135	0.435	0.100	0.182
0.557	100	100	-0.130	0.435	0.025	0.443
0.678	100	100	-0.130	0.435	0.050	0.322
0.748	100	100	-0.130	0.435	0.075	0.252
0.796	100	100	-0.130	0.435	0.100	0.204

The sample size calculation shows that with a power range of 80% to 90%, a global lymph-node effect is detectable when the GMT ratio is between 64% (approximately -0.19 on  $\log_{10}$  scale) and 74% (-0.13) pooling 4 variants of B test strains together and using a 1-sided false-positive error rate of 10%.

A decrease in GMT ratios below 74% is acceptable as, for a lower mean ratio, the presence of a marginal lymph-node effect can be compensated with an increase in sample size in a formal non-inferiority study.

Assuming a rare event occurring at the rate of 1 out of 100, a sample size of 500 subjects in the study will have a probability of 99.3% to detect a rare AE.

A total of approximately 500 subjects (approximately 100 subjects in each group) are planned for enrollment into the study.

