### **9.2. Subject withdrawal**

Subjects withdrawn from the study will not be replaced.

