#### Criteria for the Statistical Test

rMenBOMV+ACWY\_S will be declared statistically inferior if the 2-sided 80% confidence intervals (CIs) of the ratio of the GMT with rMenBOMV+ACWY\_D as control is lower than 1. The lymph-node effect would therefore be the most probable cause for the decrease observed.

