### ANCOVA2

- The fixed-effect model will include age strata, study group, strain\*\* and center as fixed effects. The pre-vaccination (Baseline) log-transformed titer with centering at zero will be included as a continuous covariate. An interaction between strain\* and pre-vaccination log-transformed titer centered at zero will be included in the model.
- The model will be fitted to the serogroup B test strain data only.

\*\* a categorical variable will be used to indicate if the dependent variable (response) is for serogroup B test strain M14459, 96217, NZ98/254 or M07-0241084.

For each study group, adjusted GMTs, SEs and 80% CI for GMT will be obtained by taking the anti-logarithm of the least squares means, the SE and the lower and upper limits of the 80% CIs of the log-transformed titers. The pre-vaccination log-transformed titer will be zero centered as follows: *log-transformed titer for each subject at Baseline – mean(log-transformed titer for all subjects at Baseline)* i.e. centering will occur after the titer results have been log transformed.

The contrasts in Table 6 will be computed at AVISIT 4 based on PPS3 to investigate possible effects on the immune response based on strains common to each study group.

No adjustment will be made for multiple comparisons.

rMenBOMV+ACWY\_S will be declared statistically inferior if the 2-sided 80% CIs of the ratio of the GMT with rMenBOMV+ACWY\_D as control is lower than 1 at 1 month after last vaccination. The lymph-node effect would therefore be the most probable cause for the decrease observed.

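### The power range of 80% to 90% given for GMT ratios of 74% to 64% is wrong at the 64% end: the plan's own inputs give about 96% to 97% there, and 90% is reached at a ratio of about 69.5%.

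*Protocol*

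**What the plan says.** Protocol section 10.4 sets out the calculation for the pooled serogroup B comparison. It states that "group sample sizes of 100 in each study group will achieve a power of approximately 80"% for a difference of -0.130 on the log10 scale (ratio 74%), with a standard deviation of 0.435 in both groups and "a significance level (alpha) of 10% using a 1-sided 2-sample equal-variance t-test". It reports the GMT ratios of MenABCWY to MenB in the previous study used for planning as running from 74% to 50%, "with a mean of 64"% (-0.19).

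Table 14 gives power for four differences (-0.130 to -0.145) at four alpha levels. Below it, the text says that the calculation shows that "with a power range of 80% to 90%, a global lymph-node effect is detectable when the GMT ratio is between 64"% (about -0.19) and 74% (-0.13), "using a 1-sided false-positive error rate of 10"%. SAP section 4.1 repeats that sentence but gives neither Table 14 nor the standard deviation.

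The decision rule is in Protocol section 10.8 and SAP section 8.1.1: the same-arm group "will be declared statistically inferior if the 2-sided 80% confidence intervals (CIs) of the ratio of the GMT", with the different-arm group as control, lies below 1.

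**The concern.** A range of power is set beside a range of ratios. The 80% end matches the 74% end, so a reader will pair 90% with 64%. Between those ratios the difference grows from 0.13 to 0.19, nearly half as much again, and a gain of only ten points in power looks too small. Table 14 cannot settle it: at alpha 10% it stops at -0.145 with power 0.858, and it has no row at -0.19 and none at 90%.

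The 64% figure matters because it is the mean ratio in the planning study. Section 10.4 says its purpose is to describe what the sample size can show. Anyone using it to judge which effect sizes a null same-arm versus different-arm result makes unlikely would take the chance of missing a 64% ratio to be 10%.

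**Working it through.** **Inputs, all from Protocol section 10.4.** n = 100 per group; standard deviation 0.435 (log10) in both groups; 1-sided alpha 0.10; two-sample equal-variance t-test.

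**Formula.** Standard error of the difference = 0.435 × √(2/100) = 0.06152. Noncentrality = |difference| / 0.06152. Degrees of freedom = 198 and critical value = 1.286. Power is the probability that a noncentral t variable with these parameters exceeds 1.286.

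**Reproducing the plan.** At -0.130 the noncentrality is 2.113 and power is 0.7960; Table 14 prints 0.796. All 16 rows of Table 14 reproduce to three decimals, so the method is the plan's own.

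**Extending it to the ratios in the sentence.**

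| Difference (log10) | GMT ratio | Noncentrality | Power |
|---|---|---|---|
| -0.130 | 74.1% | 2.113 | 79.6% |
| -0.1308 | 74.0% | 2.126 | 79.9% |
| -0.145 | 71.6% | 2.357 | 85.8% |
| -0.158 | 69.5% | 2.568 | 90.0% |
| -0.1804 | 66.0% | 2.932 | 95.0% |
| -0.190 | 64.6% | 3.089 | 96.4% |
| -0.1938 | 64.0% | 3.151 | 96.9% |

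The gap at the 64% end is 6.4 to 6.9 percentage points, too large for rounding. The probability of missing the effect is 100 - 96.4 = 3.6% at -0.19 and 100 - 96.9 = 3.1% at exactly 64%.

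**Could other inputs explain the stated range?**

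- *Another alpha.* At -0.19, 1-sided 2.5%, 5% and 7.5% give 86.7%, 92.4% and 95.0%. None is 90%, and Table 14 shows power at -0.13 falling to 55.7%, 67.8% and 74.8%.
- *The 80% interval rule.* A 2-sided 20% test, matching that rule, gives the same 96.4% at -0.19.
- *A smaller sample.* 90% at -0.19 needs 70 per group (90.2%), where power at -0.13 is 68.5%.
- *A larger standard deviation.* 90% at -0.19 needs about 0.523, where power at -0.13 is about 68%.
- *Losses.* The documents state no loss rate. Assumed losses from the per-protocol set of 5%, 10% and 15% (95, 90 and 85 per group) give 95.7%, 95.0% and 94.0% at -0.19, and 78.0%, 76.4% and 74.6% at -0.13.

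None of these gives 80% at 74% together with 90% at 64%.

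**The case against.** The strongest reply is that the sentence never says 90% at 64%. It contains no word that ties the ends together. Read literally, it could mean only that the ratios giving 80% to 90% power lie somewhere between 64% and 74%. That is true: those ratios are 74.0% and 69.5%. It remains true under the assumed losses (73.4% and 68.8% with 95 per group; 72.1% and 67.4% with 85). It is fair that the 10% miss probability is implied and not written. But this reading leaves the 64% limit with no meaning, while the 74% limit coincides with 80% power and 64% is the planning study's mean ratio. Pairing the ends is the natural reading.

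It can also be said that the consequence is small, and much of this stands. The 64% was seen for MenABCWY against MenB, not for same-arm against different-arm injection. A null result will be read mainly from the reported ratio and its 80% interval. The sample size is declared exploratory and all analyses descriptive, and no decision uses the 64% figure. These points limit the consequence to interpretation; they do not make the figure right.

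Finally, 96% to 97% is not exactly the power of the planned analysis. The pooled contrast comes from a repeated-measures ANCOVA, and on the analysis set the SAP says "The contrasts in Table 6 will be computed at AVISIT 4 based on PPS3", while the Protocol says "Subjects withdrawn from the study will not be replaced". Exclusions would lower power and covariate adjustment may raise it. The same reservation applies to every figure in section 10.4, so the corrected sentence should say that it refers to evaluable subjects.

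**Conclusion.** The concern holds. The 80% end of the range is right and the 90% end is not. Power at the lower ratio is understated by 6.4 to 6.9 points, and the implied miss probability of 10% is about three times the computed 3.1% to 3.6%. A null same-arm versus different-arm comparison would be stronger evidence against an effect of that size than the text suggests. The figures rest on the plan's standard deviation of 0.435, 100 evaluable subjects per group and the simple t-test used for planning, with no allowance for exclusions or for covariate adjustment. The error is conservative and affects interpretation only.

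**What to change.** In Protocol section 10.4 and SAP section 4.1, replace the sentence giving the power range with:

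> With 100 evaluable subjects per group, SD 0.435 and a 1-sided 10% error rate, power is about 80% at a GMT ratio of 74% (-0.13), 90% at 69.5% (-0.158) and 96% at -0.19 (ratio about 64.6%; 97% at exactly 64%).

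The word *evaluable* shows that nothing is allowed for exclusions from the per-protocol set. The cost is one sentence in each document. Enrollment, Table 14, the test and the decision rule stay as they are, and the power stated at 64% becomes more favourable.

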## 10.5.      Analysis sets

### 10.5.1.    All Enrolled Set

All subjects who signed an informed consent, underwent screening procedures, and have a subject number assigned.

**10.5.2. All Exposed Set**

All subjects in the All Enrolled Set who receive *any* study vaccination. (*Amended 29 Aug 2018*)

**10.5.3. Safety Set****10.5.3.1. Solicited Safety Set (solicited local and systemic adverse events and other solicited adverse events)**

All subjects in the All Exposed Set with any solicited AE data.

**10.5.3.2. Unsolicited Safety Set (unsolicited adverse events)**

All subjects in the All Exposed Set who attended at least 1 visit or had at least 1 safety call or at least 1 follow-up event (such as withdrawal from the study) after receiving any study vaccination.

**10.5.3.3. Overall Safety Set**

All subjects who are in the Solicited Safety Set and/or Unsolicited Safety Set.

Subjects will be analyzed as “treated” (i.e. according to the vaccine[s] a subject received, rather than the vaccine[s] to which the subject may have been randomized).

**10.5.4. Full Analysis Set, Immunogenicity**

Each Full Analysis Set (FAS) will be defined by visit and by serogroup.

**10.5.4.1. Full Analysis Set 1**

All subjects in the All Exposed Set who provided evaluable serum samples and whose assay results are available for at least 1 serogroup *or B strain* at Visit 4 for all study groups except the MenACWY group, or at Visit 2 for the MenACWY group. (*Amended 29 Aug 2018*)

**10.5.4.2. Full Analysis Set 2**

All subjects in the All Exposed Set who provided evaluable serum samples and whose assay results are available for at least 1 serogroup *or B strain* at Visit 2 for all study groups except the MenACWY group. (*Amended 29 Aug 2018*)

**10.5.4.3. Full Analysis Set 3**

All subjects in the All Exposed Set who provided evaluable serum samples and whose assay results are available for at least 1 serogroup *or B strain* at Visit 4 for all study groups except the MenACWY group, or at Visit 2 for the MenACWY group, and at baseline for all study groups. (*Amended 29 Aug 2018*)

#### 10.5.4.4. Full Analysis Set 4

All subjects in the All Exposed Set who provided evaluable serum samples and whose assay results are available for at least 1 serogroup *or B strain* at Visit 2 and at baseline for all study groups except the MenACWY group. *(Amended 29 Aug 2018)*

#### 10.5.5. Per-Protocol Set, Immunogenicity

Per-Protocol Set (PPS) 1, PPS 2, PPS 3, and PPS 4 are the corresponding subsets of FAS 1, FAS 2, FAS 3, and FAS 4, respectively, who have no major protocol violations.

A major deviation is defined as a protocol deviation that is considered to have a significant impact on the immunogenicity result of the subject.

All protocol deviations will be identified prior to the analysis and a clinical judgment will be necessary to classify each deviation as “major” or not. These deviations and the judgment regarding their use will be listed and summarized in the final report.

A list of key major deviations is provided below, but not limited to:

- Subjects enrolled who did not meet entry criteria including age at enrollment
- Subjects incorrectly vaccinated
- Subjects who did not receive study vaccinations as planned in protocol
- Subjects who did not have blood draws as planned in protocol
- Subjects with a blood draw outside of allowed time window
- Subjects with a vaccination done outside of allowed time window

These key major deviations will be assessed based on the data collected in the eCRFs. The complete list of protocol deviations considered major for this study will be detailed in the statistical analysis plan and be reported in the final report.

#### 10.5.6. Other analysis sets

No additional analysis sets are planned.

#### 10.5.7. Subgroups

There are no intended subgroups for analysis.

### 10.6. Derived and transformed data

- Immunogenicity
  - The assay cut-off values will be defined by the laboratory before analysis and will be documented in a protocol amendment or in the clinical study report.
  - For the primary and secondary endpoints (see Section 10.1 and Section 10.2, respectively), the percentage of subjects with hSBA titers  $\geq$  LLOQ and with a

4-fold increase in hSBA titers against each of the *N. meningitidis* serogroup B test strains and against *N. meningitidis* serogroups A, C, W-135, and Y will be determined.

- The GMT calculations are performed by taking the anti-log of the mean of the log concentration/titer transformations. Values to be used for the antibody concentrations/titers below the assay cut-off will be described in the statistical analysis plan.
- Handling of missing data: for a given subject and a given immunogenicity measurement, missing or non-evaluable measurements will not be replaced.
- Reactogenicity and Safety
  - Handling of missing data: for safety analyses, subjects who missed reporting symptoms (solicited/unsolicited) or concomitant medications will be analyzed further. The main safety analyses will contain missing data (missing safety values will not be imputed) but further analyses to assess the missing mechanism will be specified in the statistical analysis plan.
  - For the analysis of solicited symptoms, missing or non-evaluable measurements will not be replaced. Therefore the analysis of the solicited symptoms based on the All Exposed Set will include only subjects/doses with documented safety data (i.e. symptom screen/sheet completed).
  - Solicited AEs will be assessed as described in [Table 12](#) and Section [10.9.2](#).

## 10.7. Analysis of demographics

Demographic characteristics (age, gender, and ethnic origin) will be tabulated per study group for each analysis set as described in the statistical analysis plan.

The mean of continuous variables (plus range and SD) of the enrolled subjects, as a whole and per study group, will be calculated.

The distribution of discrete variables will be tabulated as a whole and per study group as described in the statistical analysis plan.

